## FLOWCHARTS

### Flowchart for Course 1

Trial Periods	Screen	Treatment and observation/rest										EOT	FU
Course *		1											
Week		1		2		3		4		5		6	7
Visit **	Screen	1	2	3	8	9	10	15	17	22	29	36	43
Days	-14 to -1	1	2	3	8	9	10	15	17	22	29	36	43
Informed consent	x												
Demographics	x												
Medical history	x												
Review of in-/exclusion criteria	x	x 1											
Eligibility for trial	x												
12-lead ECG	x												
Height	x												
Weight	x	x	x	x	x	x	x	x	x	x	x	x	
Physical examination, incl. tumour size (lymph nodes, spleen, liver),	x	x								x			x
Vital signs 	x	x	x	x	x	x	x	x	x	x	x	x	x
Dose assignment	x 												
Concomitant therapy	x	x	x	x	x	x	x	x	x	x	x	x	x
General safety laboratory parameters 	x	x	x	x	x	x	x	x	x	x	x	x	x
Administration of BI 836826		x		x			x		x	x			
Screening for Tumour Lysis Syndrome 		x	x		x	x							
Adverse events		x	x	x	x	x	x	x	x	x	x	x	x
Disease/response assessm. (clinical/imaging)	x	x 6							x 				x 
Serum pregnancy test 	x	x							x				
CMV monitoring 	x	x					x		x	x	x	x	x
Lymphocyte typing (B/T/NK cells)		x		x	x		x	x	x	x	x	x	x
Virology screening  (HBV, HCV, HIV, CMV)	x												
CT scan of neck, thorax, abdomen and pelvis	x 												

Proprietary confidential information.

© 2016 Boehringer Ingelheim International GmbH or one or more of its affiliated companies. All rights reserved.

This document may not - in full or in part - be passed on, reproduced, published or otherwise used without prior written permission.

EOT: End of treatment visit, to be performed at withdrawal from further treatment (<12 administrations) or at the latest 8 weeks after the last administration of BI 836826 (12 administrations)

FU: Follow-up visits (starts after EOT) at least every 6 weeks until 6 months after EOT visit, details see [section 6.2.3.2](#)

CMV: Cytomegalovirus

HBV: Hepatitis B virus

HCV: Hepatitis C virus

HIV: Human immunodeficiency virus

\* the planned duration of course 1 is 7 weeks (49 days)

\*\* the visit number follows the course number, i.e. visit 2 course 1 will read C1\_V2 and visit 2 course 2 will read C2\_V2 ...

- 1 Review of eligibility
- 2 For details during and after infusion of BI 836826, refer to [section 5.2.5.1](#)

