- 4 Assessment can be performed prior to visit 10, if CT scan from visit 9 is available.
- 5 For women of childbearing potential only (please refer to sections [3.3.3](#) (exclusion criterion 20) and [5.2.3.1](#))
- 6 For details refer to [section 5.2.3.1](#)
- 7 Screening for tumour lysis syndrome in between safety laboratory assessments ([section 5.2.3.2](#))
- 8 Quantitative CMV DNA PCR ([section 5.2.3.3.2](#))

Proprietary confidential information.

© 2016 Boehringer Ingelheim International GmbH or one or more of its affiliated companies. All rights reserved.

This document may not - in full or in part - be passed on, reproduced, published or otherwise used without prior written permission.

Flowchart for Course 3, End of Treatment visit and Follow-up

Trial Periods	Treatment and observation/rest									EOT	FU
Course *	3										
Week	15	16	17	18	19	20	21	23	25	see 	
Visit **	1	2	3	4	5	6	7	8	9		
Days	1	8	15	22	29 (+2)	36 (+5)	43 (+5)	57 (±5)	71 (±5)		
Eligibility for course 3	x 										
Vital signs 	x	x	x	x	x	x	x	x	x	x	x
Weight	x	x	x	x	x	x	x	x	x	x	x
Physical examination, incl. tumour size (lymph nodes, spleen, liver),	x			x			x			x	x
Disease / response assessment (clinical/imaging)	x			x 						x	x 
Serum pregnancy test 	x			x						x	
Concomitant therapy	x	x	x	x	x	x	x	x	x	x	x 
General safety laboratory parameters 	x	x	x	x	x	x	x	x	x	x	x
Administration of BI 836826	x	x	x	x							
Screening for Tumour Lysis Syndrome 	x	x									
Adverse events	x	x	x	x	x	x	x	x	x	x	x 
CMV monitoring 	x	x	x	x	x	x	x	x	x	x	x
Lymphocyte typing (B/T/NK cells)	x	x	x	x	x	x	x	x		x	x
CT scan of neck, thorax, abdomen and pelvis									x	x 	
12-lead ECG										x	
Completion of active trial treatment										x	
Status (remission, progression, death)										x	x
Other therapy for lymphoma										x	x

EOT: End of treatment visit, to be performed at withdrawal from further treatment (<12 administrations) or at the latest 8 weeks after the last administration of BI 836826 (12 administrations)

FU: Follow-up visits (starts after EOT) at least every 6 weeks until 6 months after EOT visit, details see [section 6.2.3.2](#)

CMV: Cytomegalovirus

\* the planned duration of course 3 is 12 weeks (84 days)

\*\* the visit number follows the course number, i.e. visit 2 course 1 will read C1\_V2 and visit 2 course 2 will read C2\_V2 ...

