1 Can be performed within 7±2 days prior to this visit

2 For details during and after infusion of BI 836826, refer to [section 5.2.5.1](#)

3 Disease / response assessment will be based on clinical judgement when recent CT is not available

4 For women of childbearing potential only (please refer to [sections 3.3.3](#) (exclusion criterion 20) and [5.2.3.1](#))

5 Concomitant therapy during FU only in case indicated for treatment of an AE (section [4.2.1](#))

6 For details refer to section [5.2.3.1](#)

7 Screening for tumour lysis syndrome in between safety laboratory assessments (section [5.2.3.2](#))

8 For AE assessment during FU refer to sections [5.2.1](#) and [6.2.3.2](#)

Proprietary confidential information.

© 2016 Boehringer Ingelheim International GmbH or one or more of its affiliated companies. All rights reserved.

This document may not - in full or in part - be passed on, reproduced, published or otherwise used without prior written permission.

9      Quantitative CMV DNA PCR (section [5.2.3.3.2](#))

11     In case end of treatment occurs before week 26, a CT scan can be performed at the EOT visit if clinically indicated for response assessment (*e.g.* progression)

12     If 12 infusions has been administered the EOT should be performed at the latest in week 26 (day 77±5 of course 3)

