## 6.2.2 Treatment periods

The treatment is given in courses with 4 administrations of a weekly infusion followed by observation/rest. Patients can receive up to three courses, *i.e.* 12 administrations. The duration of the first two courses is 7 weeks and for the third course 12 weeks, hence a 3-week or an 8-week observation/rest after the infusions of BI 836826.

### 6.2.2.1 Course 1

In the first course there are 4 visits with treatment and 6 visits for safety assessment. The first two administrations are given as an in-hospital stay for safety, tumour lysis assessment

Between the visits with infusion of BI 836826 safety visits will be performed. After last infusion the safety visits will be weekly. Clinical disease assessment will be performed at the first infusion visit (visit 1) and the last infusion visit (visit 7) as well as the last visit in the course (visit 10).

For details see [flowchart](#) for Course 1.

In case of the split first dose administration patients are required to be hospitalized under close surveillance with access to intensive care for at least 72 hours after the start of the low dose of BI 836826 to allow close monitoring for infusion-related reactions. Please refer the flowchart in [section 10.7](#) for clinical disease, safety

### 6.2.2.2 Course 2

In the second course there are 4 visits with treatment and 6 visits for safety and response assessment. The first administration is given as an in-hospital stay for safety, tumour lysis assessment

Between the visits with infusion of BI 836826 safety visits will be performed. After last infusion the safety visits will be weekly. Clinical disease assessment will be performed at the first infusion visit (visit 1) and the last infusion visit (visit 7). A CT scan of neck, thorax, abdomen and pelvis must be performed at visit 9 to be available for the disease assessment and response evaluation that are planned to be done at the last visit in the course 2 (visit 10).

For details see [flowchart](#) for Course 2.

### 6.2.2.3 Course 3

In the third course there are 4 visits with treatment and 5 visits for safety and response assessment. All infusions can be given as out-patient, if recent previous infusions have been well tolerated. Clinical disease assessment will be performed at the first (visit 1) and at the last infusion (visit 4).

Proprietary confidential information.

© 2016 Boehringer Ingelheim International GmbH or one or more of its affiliated companies. All rights reserved.

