for all analyses. In laboratory listings, the CTCAE grade will be displayed as -1.

Patients with hepatic enzyme elevation will be tabulated.

Patients with possibly clinically significant laboratory values will be tabulated (see [Section 9.2](#)).

The prioritized laboratory values (see [Section 5.4.5.1](#)) will be displayed in Section 15 of the final CTR while all other laboratory parameters will be displayed in the Appendix of the CTR.

Neutropenia, thrombocytopenia and leukopenia

Episodes of low neutrophil, platelet and WBC counts are of special interest. Episodes with CTCAE grade 3/4 as well as episodes with CTCAE grade 4 lasting 7 or more days will be analysed separately.

An episode of low blood counts of grade 4 starts with the first occurrence of a CTCAE grade 4 and lasts until the first time the CTCAE grade falls back to <=3 (analogously for an episode of CTCAE grade 3/4).

In case the episode starts during the EOT or Follow-up, the duration of this episode is defined to be missing. The reason for this approach is that after the EOT laboratory data is only

captured infrequently and therefore the duration of an episode would be overestimated due to lack of data.

If an episode starts before EOT and the CTCAE grade of the respective parameter does not fall back to the respective grade that ends the episode and the patient dies, the end of the episode is defined by the date of death. If the episode starts before EOT and lasts during Follow-up, the episode is censored with the date of DBL.

Number of patients with respective episodes, number of episodes, episodes per patient, duration of individual episode, number of episodes divided by number of infusion per patient, mean and median duration of episode per patient will be displayed.

Additionally, a frequency table displaying number of patients with episode of neutropenia Grade 4 and concomitant AEs in the UDAEC Infections (incl. respiratory infections and sepsis) of any grade as well as only for Grade 3 or 4 infections will be provided. In this context, concomitant AE is defined as AE with onset date within the neutropenia episode. This will be also done for CD4+ T-cell count Grade 4 and concomitant CD4 related specific infections from the UDAEC CD4 related specific infections.

The same way, a frequency table displaying number of patients with episode of thrombocytopenia Grade 4 and concomitant AEs in the UDAEC bleeding of any grade as well as only for Grade 3 or 4 bleeding will be provided.

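### SAP 7.8.2: the 7-day cut for prolonged Grade 4 cytopenia equals the planned sampling interval, so most isolated Grade 4 values in rest periods and course 3 are classed as prolonged

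*SAP*

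**What the plan says.** SAP 7.8.2 (paragraphs on neutropenia, thrombocytopenia and leukopenia) defines an episode from the observed samples. Its start: "An episode of low blood counts of grade 4 starts with the first occurrence of a CTCAE grade 4". Its end: it "lasts until the first time the CTCAE grade falls back to <=3". The SAP then states that "episodes with CTCAE grade 4 lasting 7 or more days will be analysed separately". Planned displays include the number of patients with episodes, the duration of each episode, and the mean and median duration per patient.

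The same section sets duration to missing for episodes that start at EOT or in follow-up. Its reason is that infrequent sampling after EOT would make durations too long. No such rule applies before EOT. No day-count convention is given for these episodes, whereas PFS and FFS in SAP 5.2.2 are end minus start plus 1.

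The sampling schedule is in the protocol. Section 6.2.2 says of courses 1 and 2: "After last infusion the safety visits will be weekly". Of the rest periods it says "hence a 3-week or an 8-week observation/rest after the infusions of BI 836826", meaning 3 weeks after courses 1 and 2 and 8 weeks after course 3. The flowcharts require safety laboratory at each visit. In course 3 these are days 1, 8, 15, 22, 29, 36, 43, 57 and 71. After 12 infusions, EOT falls at the latest at "day 77±5 of course 3".

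**The concern.** The threshold that defines a prolonged episode is the same length as the planned gap between samples. A single Grade 4 count followed by a recovered count one week later is recorded as lasting 7 days, whether the true low period was one day or six. In that part of the schedule the category cannot tell a brief dip from sustained cytopenia.

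This matters for interpreting dose. SAP section 3 says that 3 of the 4 Korean patients in the 100 mg expansion developed infections with Grade 4 neutropenia and that the expansion was stopped. Protocol 5.2.1.1 does not count haematological events themselves as DLTs, but it takes them into account when the dose for further development is chosen. The SAP's tables of infections and bleeding during Grade 4 episodes use the same episode end, so a late end date also widens the window in which an event counts as concomitant.

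**Working it through.** **1. Planned gaps.** Courses 1 and 2 last 49 days, so day 1 of the next course is day 50. Recorded duration of an isolated Grade 4 value = next sample day minus its own day.

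| Period | Nominal sample days | Gaps (days) |
|---|---|---|
| Course 1 dosing weeks | 1, 2, 3, 8, 9, 10, 15, 17, 22 | 1, 1, 5, 1, 1, 5, 2, 5 |
| Courses 1 and 2, rest | 22, 29, 36, 43, 50 | 7, 7, 7, 7 |
| Course 3 to day 43 | 1, 8, 15, 22, 29, 36, 43 | 7 throughout |
| Course 3, late | 43, 57, 71, EOT 77 | 14, 14, 6 |

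The rest-period gaps reproduce the protocol's own weekly figure. At nominal spacing every isolated Grade 4 value in rows 2 and 3 is recorded as 7 days. Values on days 43 and 57 of course 3 are recorded as 14 days. The exceptions are course 3 day 71 (6 days, or 7 with a plus-1 count) and the course 1 dosing weeks, where the largest gap is 5 days.

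**2. Short episodes at exact spacing.** For true duration D shorter than the interval T and uniform onset, P(detected) = D/T and recorded duration = T.

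- T = 7: D = 1, 3, 5 days are detected with probability 1/7 = 14%, 3/7 = 43%, 5/7 = 71%. All detected episodes are recorded as 7 days.
- T = 14: detection is 1/14 = 7%, 3/14 = 21%, 5/14 = 36%. All detected episodes are recorded as 14 days.

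**3. Visit windows.** In course 2, day 29 is ±2, day 36 is ±5 and day 43 is ±2. Gaps can then be 5-9 days (22 to 29, 43 to 50) or 1-14 days (29 to 36, 36 to 43). Of the in-window day pairs, 60% and 56% respectively are at least 7 days apart (80% and 65% with a plus-1 count). With visit days uniform in their windows and onset uniform over days 22-43, simulation gives:

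| True duration (days) | Detected | Classed as 7 days or more | Same, plus-1 count |
|---|---|---|---|
| 1 | 12% | 66% | 73% |
| 3 | 38% | 63% | 75% |
| 5 | 63% | 65% | 78% |
| 6 | 72% | 67% | 80% |

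In course 3 the day 22 to 29 gap is always 7-9 days, because day 29 may only move later. Later in that course the windows allow gaps below 7 days (for example 2-12 days from day 36 to 43). Course 1 windows are not legible in the flowchart, so course 2 windows stand in for them.

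**4. Effect on durations (illustration).** Assume exact weekly sampling, uniform onset and exponential true duration with mean m. Let q = exp(-7/m).

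- P(detected) = (m/7)(1 - q)
- Share of detected episodes truly lasting 7 days or more = 7q / [m(1 - q)]
- Mean recorded duration among detected = 7/(1 - q)
- Mean true duration among detected = 2m - 7q/(1 - q)

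| m (days) | q | Truly 7 days or more | Recorded as such | Mean recorded | Mean true |
|---|---|---|---|---|---|
| 3 | 0.097 | 25% | 100% | 7.8 | 5.2 |
| 4 | 0.174 | 37% | 100% | 8.5 | 6.5 |
| 6 | 0.311 | 53% | 100% | 10.2 | 8.8 |
| 10 | 0.497 | 69% | 100% | 13.9 | 13.1 |

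P(detected) times mean recorded duration = (m/7)(1 - q) × 7/(1 - q) = m. So the mean over all episodes, with undetected ones counted as zero, equals the true mean. The distortion sits in the category and in durations among detected episodes.

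**5. The lower bound as classifier.** Suppose an episode counted as prolonged only when its Grade 4 samples span at least 7 days. Under the model in step 4, the share of truly prolonged episodes missed is 1 - (m/7)(1 - q) = 61%, 53%, 41% and 28% for m = 3, 4, 6 and 10. A true 10-day episode would be flagged with probability (10 - 7)/7 = 43%.

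**The case against.** A reader might infer that any isolated Grade 4 value becomes a prolonged episode, so that over-reporting is built in throughout. The documents do not support that. Visit windows allow rest-period gaps below 7 days, day 71 to EOT is nominally 6 days, and course 1 dosing weeks are sampled densely. The flowchart is also a minimum: protocol 4.1.4.3 relies on frequent counts to find prolonged neutropenia, and 5.2.3.1 allows extra visits when a course is delayed. These points stand and limit the scope. They do not remove the problem, because the required minimum during a delay is again one visit a week and the windows still leave about two thirds of detected short episodes misclassified.

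A second tempting inference is that reported mean durations mainly reflect visit spacing and that cohorts cannot be compared. That also goes too far. Late start dates and missed short episodes offset late end dates, and the excess at a true mean of 10 days is 13.9 against 13.1, about 6%. All cohorts follow essentially the same schedule, so the recording error is largely shared, and nothing in the documents shows sampling that differs by dose or ethnicity.

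Third, the analysis is descriptive, and the 7-day row is one display among several. Individual episode durations and time courses of neutrophils, WBC and platelets are also planned, and the infection table uses Grade 4 episodes of any length. That limits the consequence. A reader of the prolonged-episode table alone would still not see how many entries rest on one sample.

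Finally, the SAP rule errs towards counting more toxicity, which is the safer direction for a safety table. This is a sound reason not to replace it (step 5), but no reason to leave the lower bound out.

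**Conclusion.** The point holds for the rest periods of courses 1 and 2 and for course 3. There the prolonged Grade 4 category cannot separate a one-off low value from sustained cytopenia. At exact nominal spacing all isolated values in those periods are classed as prolonged, except at course 3 day 71. With course 2 windows the figure is about 63-67% of detected true 1-6 day episodes, or 73-80% with a plus-1 count. The SAP's own safeguard against overestimation begins only at EOT, although course 3 already has 14-day gaps before then.

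The window figures assume uniform visit timing and onset, and the duration table assumes exponential lengths and exact weekly sampling. The documents give neither a duration distribution nor actual sampling dates, so the size of the effect in this trial is unknown. The case is for a fuller display and does not show that the planned tables are unusable.

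**What to change.** In SAP 7.8.2:

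- Keep the present rule (first Grade 4 sample to first sample of Grade 3 or lower) and label it the upper bound. The existing rules for death, follow-up and EOT can stay.
- Beside it, report the lower bound: first to last Grade 4 sample of the same episode.
- Give the count of episodes lasting 7 days or more under both bounds.
- Show single-sample episodes in their own row.
- State the day-count convention (end minus start, or plus 1), and note that planned counts before EOT are up to 14 days apart.

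Do not make the lower bound the sole classifier, since it would miss many truly prolonged episodes. The cost is SAP wording, one extra derived variable and a slightly longer table. No new samples or visits are needed.

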### 3.3.3 Exclusion criteria

- 1. Primary central nervous system (CNS) lymphoma or known CNS involvement
- 2. Prior history of malignancy other than a mature B cell neoplasm according to WHO classification ([R10-6296](#)) (except basal cell or squamous cell carcinoma of the skin, or carcinoma *in situ* of the uterine cervix or breast treated with curative therapy) unless the subject has been free of disease and without treatment for at least 5 years
- 3. Last chemotherapy  $< 4$  weeks prior to visit 1
- 4. Last anti-CD20 therapy (non-radiolabelled)  $< 4$  weeks prior to visit 1
- 5. Last corticosteroid  $< 2$  weeks prior to visit 1 unless the dose is  $\leq 10$  mg/day prednisolone or equivalent
- 6. High-dose therapy with stem cell support  $< 6$  months prior to visit 1
- 7. Radio-immunotherapy  $< 3$  months prior to visit 1
- 8. Prior allogeneic stem cell transplant (this criterion applies only for the dose-escalation cohorts)
- 9. AST or ALT  $> 2.5 \times$  upper limit of normal (CTCAE grade 2 or higher)
- 10. Total bilirubin  $> 1.5 \times$  upper limit of normal (CTCAE grade 2 or higher)
- 11. Absolute neutrophil count  $< 1.0 \times 10^9/L$  (without growth factor support)
- 12. Platelets  $< 25 \times 10^9/L$  (without growth factor support or transfusions)
- 13. Calculated GFR  $< 45$  mL/min (see [appendix 10.5](#))
- 14. Proteinuria CTCAE grade 2 or higher

Proprietary confidential information.

© 2016 Boehringer Ingelheim International GmbH or one or more of its affiliated companies. All rights reserved.

This document may not - in full or in part - be passed on, reproduced, published or otherwise used without prior written permission.

15. Significant concurrent medical disease or condition which according to the investigator's judgement would either compromise patient safety or interfere with the evaluation of the safety of the test drug, *e.g.* symptomatic congestive heart failure, unstable angina pectoris, cardiac arrhythmia requiring therapy with the exception of extra systoles or minor conduction abnormalities
16. Chronic or ongoing infection requiring treatment at the time of enrolment or within the previous two weeks
17. Active hepatitis B or hepatitis C, or laboratory evidence for a chronic infection with hepatitis B or C (see [5.2.3.3.1](#))
18. HIV infection
19. CMV viraemia

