#### 4.1.4.3 Management of infections:

During treatment with BI 836826 patients need to be carefully monitored for infections at each clinic visit. Frequent blood counts monitoring will help to identify patients with prolonged neutropenia who might be at risk for severe infections. It is highly recommended that the treatment of infection starts immediately upon very first clinical symptoms. Depending on investigators' assessment the use of growth factors, antibiotics, antifungals, and antivirals should be considered, and implemented with no delay. The next administration of BI 836826 needs to be delayed until the patient has cleared an infection and has recovered from neutropenia as outlined in sec: 4.1.4.4

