**Proprietary confidential information.**

**© 2016 Boehringer Ingelheim International GmbH or one or more of its affiliated companies. All rights reserved.**

This document may not - in full or in part - be passed on, reproduced, published or otherwise used without prior written permission.

continue treatment with a further infusion of BI 836826, all of the following criteria must be met:

- (1) No active infection
- (2) Neutrophils  $\geq 1000 / \mu\text{L}$  ( $1.0 \times 10^9 / \text{L}$ ) and platelets  $\geq 25.000 / \mu\text{L}$  ( $25 \times 10^9 / \text{L}$ ), with or without growth factor support or transfusions.
- (3) no evidence of progressive disease
- (4) Acceptable tolerability (in case of an adverse event at the planned start of a treatment course, patients may continue therapy only after recovery to a level which would allow further therapy, *i.e.* CTCAE grade 1 or pre-treatment value.)

In case criterion 1 and/or 4 is not fulfilled, blood counts and/or the adverse event should be re-evaluated for up to three weeks. A delay during a course should be communicated to the clinical monitor at Boehringer Ingelheim. As soon as all criteria 1-4 are met, the investigator in agreement with the clinical monitor at Boehringer Ingelheim may continue the treatment (unless other criteria for discontinuation or withdrawal apply, see [section 3.3.4.1](#)). If a visit with administration of BI 836826 is delayed, all subsequent visits with treatment administration will be recalculated based on the actual date of delayed visit. If a visit is delayed less than 5 days, the delay may be caught up by shortening the observation period of the course after agreement between investigator and clinical monitor of the trial, provided that patient fulfills all the requirement for the next treatment ([see section 6.1](#)).

In case an adverse event is continuing at a CTCAE grade 2 or higher without recovery to grade 1 within 5 weeks after the last BI 836826 infusion and this is above the pre-treatment level, the investigator in agreement with the clinical monitor at Boehringer Ingelheim may continue BI 836826 only in the case that the event is considered not drug-related by investigator and sponsor.

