#### 4.2.1.2.2 Growth factors

The use of growth factors such as granulocyte colony stimulating factor (G-CSF) will be allowed during therapy. However, growth factors are not allowed at inclusion and should be avoided, if patient's condition allows, in the first treatment weeks for better assessment of safety parameters.

Prophylactic antibiotics and antiviral drugs are allowed during therapy.

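### In SAP 7.8.2 a platelet count raised briefly by transfusion can end a Grade 4 thrombocytopenia episode, so recorded durations shorten and a prolonged episode can drop out of the 7-day category

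*SAP*

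**What the plan says.** SAP 7.8.2 (Laboratory data, text on neutropenia, thrombocytopenia and leukopenia) opens a Grade 4 episode at the first Grade 4 value. The episode "lasts until the first time the CTCAE grade falls back to <=3" ("analogously for an episode of CTCAE grade 3/4"). The section requires no confirmatory value and no minimum gap between episodes, and does not ask whether the closing value followed a transfusion.

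Several outputs rest on this rule. The SAP states that "episodes with CTCAE grade 4 lasting 7 or more days will be analysed separately". The summary is to give "Number of patients with respective episodes, number of episodes, episodes per patient, duration of individual episode", together with episodes per infusion and mean and median duration per patient. A further table counts patients with Grade 4 thrombocytopenia and a concomitant bleeding event, where the event must start inside the episode.

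The protocol foresees transfused counts. Section 4.2.1.2 includes blood products in supportive care. Section 3.3.3 (exclusion criterion 12) judges entry platelets "without growth factor support or transfusions". On treatment, section 4.1.4.4 accepts platelets for the next infusion "with or without growth factor support or transfusions".

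**The concern.** A platelet transfusion can raise a count for a short time while the underlying thrombocytopenia continues. Under the SAP rule the raised value closes the episode, and the next fall opens a new one. One long episode is then recorded as several shorter ones.

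The re-treatment rule makes this foreseeable, because dosing days are when a transfused count is most likely to be sought and measured. The outputs at stake are recorded duration, the number of patients with a Grade 4 episode of 7 days or more, and the bleeding table, since a bleed that starts in a transfused gap is not counted as concomitant. Protocol 5.2.1.1 excludes haematological events from the DLT definition but says that they will inform the dose for further development. These displays are therefore one of the places where a reader would look for prolonged thrombocytopenia.

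**Working it through.** The plan gives no figure on this point, so there is none to reproduce. The check applies the SAP rule to assumed count patterns.

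**Inputs from the documents**
- Rule: an episode runs from the first Grade 4 reading to the first reading of Grade 3 or lower; duration = end day − start day (SAP 7.8.2).
- Threshold for a prolonged episode: 7 days (SAP 7.8.2).
- Course 1 safety laboratory days: 1, 2, 3, 8, 9, 10, 15, 17, 22, 29, 36, 43 (protocol flowchart for course 1). Infusions are on days 1, 8, 15 and 22 (protocol 3.1).

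**Assumptions, not in the documents**
- Grade 4 at every reading from day 3 to day 22 unless raised by transfusion; Grade 3 or lower at day 29.
- A raised reading is Grade 3 or lower. The documents do not reproduce the CTCAE platelet limits.
- For the added analysis, transfusions on days 7, 14 and 21 and a 3-day window.

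**Results under the SAP rule**

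| Readings raised | Episodes (days) | Total days | Episodes ≥7 days | Patient in ≥7-day category |
|---|---|---|---|---|
| None | 29−3 = 26 | 26 | 1 | yes |
| 8, 15 and 22 | 8−3 = 5; 15−9 = 6; 22−17 = 5 | 16 | 0 | no |
| 9 only | 9−3 = 6; 29−10 = 19 | 25 | 1 | yes |
| 10 only | 10−3 = 7; 29−15 = 14 | 21 | 2 | yes |
| 15 only | 15−3 = 12; 29−17 = 12 | 24 | 2 | yes |

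In the second row, 26 − 16 = 10 days fall outside any recorded episode, and a bleed that starts on one of them is not concomitant. The conclusion does not depend on the unobserved week before day 29: the first and last observed Grade 4 readings in that row are days 3 and 17, already 17 − 3 = 14 days apart.

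**With the 3-day window.** The raised readings on days 8, 15 and 22 each come 1 day after a transfusion and are set aside. The episode runs from day 3 to day 29: one episode of 26 days.

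**Dependence on timing.** On a daily grid with a true 21-day Grade 4 period, and each transfusion raising the count for 1 to 3 days:
- every 5 days: 4 episodes, the longest 5 days, none of 7 days or more;
- every 7 days: 3 episodes, the first of 7 days and the others of 4 to 6, so the patient stays in the category;
- every 10 days: 2 episodes, of 10 and 7 to 9 days, so the patient stays in the category.

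A closing value caused by transfusion can only shorten recorded duration. The number of patients with an episode of 7 days or more can therefore fall or stay the same, but cannot rise. The number of such episodes can rise, as in the day 10 and day 15 rows.

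**The case against.** The strongest reply is that a transfused count is the count the patient actually had, and that an observed-count definition agrees with the on-treatment rule in protocol 4.1.4.4. Fragmentation would also be partly visible, since the SAP shows worst CTCAE grade, individual platelet time courses and episodes per patient. Both points stand, and they are reasons to keep the present definition and add to it.

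Scheduled sampling also limits the problem. From day 22 of course 1, and throughout course 3, laboratory visits are weekly or sparser, so a recorded episode there nominally lasts at least 7 days. Splitting into shorter pieces on scheduled days is largely confined to days 1 to 22 of courses 1 and 2. Unscheduled samples could extend it, but their frequency is not given.

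A reader might infer three stronger points that the documents do not support.

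- **That growth factor splits neutropenia episodes in the same way.** A lasting rise after G-CSF gives one shorter episode and a real recovery. Disregarding neutrophil values for a fixed time after G-CSF would label recovered patients as Grade 4 and attribute later infections to neutropenia.
- **That the Korean 50 and 75 mg cohorts will look safer than the Caucasian cohorts.** Protocol 4.1.4.3, added by amendment 4, says that, subject to the investigator's judgement, "the use of growth factors, antibiotics, antifungals, and antivirals should be considered, and implemented with no delay". Section 4.2.1.2.2 prefers to avoid growth factors, where the patient's condition permits, "in the first treatment weeks for better assessment of safety parameters". Neither passage mentions transfusion, and no rate of support by cohort is given. A difference is possible but not shown.
- **That prolonged cytopenia is under-reported overall, masking the infection signal.** The SAP ties thrombocytopenia to bleeding, not infection. In addition, episodes that begin before EOT and continue into follow-up are carried to database lock, which lengthens durations, so the net direction across the table is unknown.

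**Conclusion.** The point holds for platelets. The rule in SAP 7.8.2 can shorten recorded Grade 4 and Grade 3/4 thrombocytopenia, and can move a patient with prolonged Grade 4 out of the 7-day category. In the assumed course 1 example, one episode of 26 days becomes three of 5, 6 and 5 days. This needs a reading raised to Grade 3 or lower and then a return to Grade 4; how often that happens cannot be derived from the documents.

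The number of patients with any Grade 4 episode is unaffected, the number of episodes is the same or higher, and the DLT and MTD counts do not use these episodes. The analysis is descriptive, so this is a modest improvement to a safety display and not a flaw in the trial's primary result. SAP sections 9.2 to 9.4 and the internal laboratory guideline are not available, so a rule placed there cannot be excluded, but the definition in 7.8.2 reads as complete.

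**What to change.** In SAP 7.8.2, before database lock:

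1. Keep the current observed-count definition for all three parameters.
2. Add a pre-specified platelet analysis in which a value of Grade 3 or lower within a declared window after a transfusion does not end the episode; it ends at the first such value outside the window. Three days could serve as the window, stated as a convention.
3. Report duration, patients with a Grade 4 episode of 7 days or more, and the concomitant-bleeding table under both definitions.
4. For neutrophils and WBC, disregard no values after G-CSF. Tabulate or list, by cohort, the episodes during which growth factor was given.

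Protocol 4.2.1.3 already requires concomitant treatments and their dates in the eCRF up to EOT, so no new data collection is expected. It asks for dates and not times, so the SAP also needs a convention for a transfusion and a sample on the same day. The cost is SAP wording and some programming. The downside is that the window is arbitrary and that platelet durations become somewhat longer in the added analysis. Patient care does not change.
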